7.5.1 Pharmacodynamic and Efficacy Measurements

Pharmacokinetic, PD, and efficacy endpoints will be evaluated in all subjects. All PK and PD samples should be taken in the morning. The subject must be in a fasted state (at least 8 hours without food and drink, except water) and blood should be collected before being dosed with KRN23 and/or as one of the early procedures during study visits, as appropriate. The usual precaution for venipuncture should be observed. It is important to avoid hemolysis.

7.5.1.1 Primary Pharmacodynamic Measurements

The PD effect of KRN23 will be assessed in adults with XLH by measuring the following before KRN23 administration in a fasted state:

- Serum phosphorus (pre-dose at Weeks 0, 2, 4, 6, 8, 10, 12, 24, 26, 28, 36, 38, 40, 48, 50, 52, 60, 72, 96, 120, 144, and every 24 weeks as applicable through the EoT Visit)
- TRP (pre-dose at Week 0)
- TmP/GFR (fasting 2-hour urine; pre-dose at Weeks 0, 12, 24, 36, 48, 72, 96, 120, 144, and every 24 weeks as applicable through the EoT Visit)
- Serum intact parathyroid hormone (iPTH; pre-dose at Weeks 0, 12, 24, 36, 48, 72, 96, 120, 144, and every 24 weeks as applicable through the EoT Visit)
- Serum FGF23 (pre-dose at Weeks 0, 4, 8, 12, 24, 28, 36, 40, 48, 72, 96, 120, 144, and every 24 weeks as applicable through the EoT Visit)
- Serum 1,25(OH)₂D (pre-dose at Weeks 0, 12, 24, 36, 48, 72, 96, 120, 144, and every 24 weeks as applicable through the EoT Visit)
- Bone biomarkers: ALP, BALP, CTx, and P1NP (pre-dose at Weeks 0, 24, 48, 72, 96, 120, 144, and every 24 weeks as applicable through the EoT Visit)
- 2-hour (fasting) and 24-hour urine (urinary phosphorus, creatinine, and calcium; Weeks 0, 12, 24, 36, 48, 72, 96, 120, 144, and every 24 weeks as applicable through the EoT Visit)

7.5.1.2 Exploratory Efficacy Measurements

Exploratory clinical efficacy measures will evaluate the effect of KRN23 on bone health (Section 7.5.1.2.1), PROs (Section 7.5.1.2.2), and clinical outcomes (Section 7.5.1.2.3), in adults with XLH. Refer to the study reference manual for additional details on clinical efficacy measures.

7.5.1.2.1 Bone Health Measurements

Standard radiographs will be obtained predose- at Week 0 and at Weeks 12, 24, 36, 48, 72, 96, 120, 144, and every 24 weeks as applicable through the EoT Visit until identified fractures/pseudofractures resolve. Standard radiographs will be obtained of the chest, lateral spine, right and left hand/wrist, right and left humerus, right and left radius/ulna, right and left femur/pelvis, right and left tibia/fibula, and right and left foot as well as any location(s) where the subject is currently experiencing tenderness or pain that may reflect underlying pathology, or where the subject has a history of recent (<3 months) fracture, or in bones where radiographs suggest the presence of a fracture or pseudo-fracture. Radiographs will be interpreted locally for the identification of new abnormalities, and on treatment- radiographs will be compared to Screening radiographs by 3 trained central readers (2 primary and 1 adjudicator) who are blinded to post-treatment time point and subject data. At each

on-treatment time point, the radiograph will be compared to Baseline and rated by the 3 central readers, using a pre-defined list of abnormalities. Central readers will be blinded to other patient data.

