7.6 Statistical Methods and Determination of Sample Size

The completeness of the data affects the integrity and accuracy of the final study analysis. Therefore, every effort will be made to ensure complete, accurate and timely data collection, and to avoid missing data. The procedures for handling missing, spurious, or unused data, and the detailed method for analyses will be presented in the Statistical Analysis Plan (SAP); the information below is intended as a guide to planned analyses.

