## 7 DATA SCREENING AND ACCEPTANCE

### 7.1 Handling of Missing and Incomplete Data

Missing clinical outcome data can occur for multiple reasons, including missed subject visits and scales or measures with missing item scores. Missing and incomplete data will be identified through a review of tables and listings for this study. Missing and incomplete data will be identified for investigation, and possible resolution, by Data Management prior to the study database lock.

For all analyses, missing data will be treated as missing, unless otherwise specified. When a change from baseline is assessed, only subjects with a baseline and at least one post-baseline measurement will be included in the analysis.

Depending on the number of discontinuations and missed visits from the study, a sensitivity analysis might be conducted for the pharmacodynamics and the efficacy endpoints analyses, where missing data will be imputed using mBOCF (modified Baseline Observation Carried Forward) defined as follows:

- for discontinuations due to AE or death use the worst between BOCF (Baseline Observation Carried Forward) and LOCF (Last Observation Carried Forward)
- otherwise use LOCF.

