## 8 STATISTICAL METHODS OF ANALYSIS

### 8.1 General Principles

The statistical analyses will be reported using summary tables, figures, and data listings. Statistical tests will be 2-sided at the alpha=0.05 significance level and 2-sided 95% confidence interval will be used. All p-values will be presented as nominal p-values. No adjustment on multiplicity will be made. Continuous variables will be summarized with means, standard deviations, standard errors, medians, Q1, Q3, minimums, and maximums. Categorical variables will be summarized by counts and by percentages of subjects in corresponding categories. No imputation on missing data will be made, unless stated otherwise. All data obtained from the CRFs as well as any derived data will be included in data listings.

The Week 24 analysis will be performed when all patients enrolled in the study have completed the Week 24 visit or have discontinued the study. The final analysis will be conducted when all patients enrolled in the study have completed the Week 72 visit or have discontinued the study.

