### 8.8.2.2 X-Ray Endpoints

The number, the change from baseline and the location of the active pseudofractures or other disease-related skeletal abnormalities as viewed on standard radiographs at each visit will be evaluated using descriptive statistics. A listing containing the X-Ray endpoints details will also be provided.

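### Filming may stop once a lesion heals, and no rule says how that lesion then counts, so the protocol's by-visit percentage healed can fall below the true healed share.

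*Protocol*

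**What the plan says.** **When filming stops.** Protocol 7.5.1.2.1 continues radiographs "every 24 weeks as applicable through the EoT Visit until identified fractures/pseudofractures resolve". Protocol 7.6.2.6, footnote 17 to Protocol Tables 2.1 and 2.2, and footnote 14 to SAP Appendix 6 also allow filming to end on healing. None says whether it ends lesion by lesion or subject by subject, or whether the local or the central reading ends it.

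**How lesions are rated.** Each rating comes from that visit's own film: at each "on-treatment time point, the radiograph will be compared to Baseline and rated by the 3 central readers" (Protocol 7.5.1.2.1).

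**The endpoint.** Protocol 7.6.1.3 asks for the numbers and percentages of baseline active pseudofractures and fractures in four categories (healed, partly healed, unchanged, worse) at post-baseline visits, summarized at each time they are observed. The Amendment 2 summary of changes (item 10) records that these categories were specified in that amendment.

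**The SAP analysis.** SAP 4.3 lists fracture healing among the exploratory endpoints. SAP 8.8.2.2, however, plans only the number, change from baseline and location of active pseudofractures or other skeletal abnormalities "as viewed on standard radiographs at each visit will be evaluated using descriptive statistics", plus a listing. The SAP amendment is dated 27 April 2016, before Protocol Amendment 2.

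**Missing data.** Protocol 7.6 leaves the procedures to the SAP, but Protocol 7.6.2.3 already rules out imputation in any analysis. SAP 7.1 agrees: "For all analyses, missing data will be treated as missing, unless otherwise specified". It illustrates missingness this way: "Missing clinical outcome data can occur for multiple reasons, including missed subject visits and scales or measures with missing item scores". Filming stopped by healing is not mentioned, and SAP 8.8.2.2 specifies nothing different for X-rays.

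**The concern.** Taken together, these rules make the presence of a film depend on the result it would show. A lesion that heals may stop being filmed, has no rating at the next visit, and is then missing under the stated rule. Successive visits would rest on different sets of lesions, with healed ones selectively removed. The reported percentage healed could decline while true healing rises or holds steady, and two analysts following the same text could report different percentages. No primary result, hypothesis test or safety conclusion is at stake.

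**Working it through.** The documents state no figure for this point, so there is nothing to reproduce. Lesion counts, healing rates and stopping patterns below are assumptions.

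**General formula.** Let p be the share of baseline active lesions truly healed at a visit, and r the share healed and no longer filmed (r ≤ p). Assume no recurrence and no dropout. Only healed lesions leave, so:
- lesions imaged at the visit as denominator: (p − r)/(1 − r), a shortfall of r(1 − p)/(1 − r);
- all baseline lesions as denominator, unfilmed ones left unscored: p − r, a shortfall of r.

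Neither can exceed p. With p = 67%:

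| r | Over imaged lesions | Over baseline lesions |
|---|---|---|
| 10% | 0.57/0.90 = 63% | 57% |
| 20% | 0.47/0.80 = 59% | 47% |
| 35% | 0.32/0.65 = 49% | 32% |

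**Small example.** Ten baseline lesions, with 4, 2, 1 and 0 newly read as healed at Weeks 12, 24, 36 and 48, each leaving filming after that reading:

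| Week | True healed | Over baseline lesions | Over imaged lesions |
|---|---|---|---|
| 12 | 40% | 4/10 = 40% | 4/10 = 40% |
| 24 | 60% | 2/10 = 20% | 2/6 = 33% |
| 36 | 70% | 1/10 = 10% | 1/4 = 25% |
| 48 | 70% | 0/10 = 0% | 0/3 = 0% |

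**Slower stopping.** Suppose filming stops only when all of a subject's k lesions have healed, healing is independent, and 20% of active lesions heal per visit. At the fifth post-baseline film p = 1 − 0.8^5 = 0.672; at the fourth, q = 1 − 0.8^4 = 0.590; and r = q^k.
- k = 2: r = 0.349; imaged (0.672 − 0.349)/(1 − 0.349) = 0.497.
- k = 3: r = 0.206; imaged (0.672 − 0.206)/(1 − 0.206) = 0.587.

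**Opposing effect.** If a share u of baseline lesions leaves the study unhealed, the imaged figure is (p − r)/(1 − r − u), which equals p when u = r(1 − p)/p. Here that is u = 0.170 for k = 2 and 0.100 for k = 3.

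**The quantity SAP 8.8.2.2 does plan.** Mean reduction in active lesions per subject, same assumptions:
- All subjects with 2 lesions: true 2 × 0.672 = 1.34; imaged 2 × 0.497 = 0.99.
- Half with 1 lesion, half with 6: true 3.5 × 0.672 = 2.35. The shares still filmed are 1 − 0.590 = 0.410 and 1 − 0.590^6 = 0.958. The mean reductions among those filmed are 0.2 and 3.947. Imaged mean: (0.410 × 0.2 + 0.958 × 3.947)/(0.410 + 0.958) = 2.82.

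The first falls below the truth and the second above it, so the direction is not fixed for this measure.

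**The case against.** The best reply is that stopping after healing is planned non-collection with a known result, not missing data. The endpoint is a percentage of the baseline active lesions, which points to a fixed denominator, and most analysts would count such a lesion as healed. That is the sensible reading, but it is unwritten. The denominator wording does not say how an unfilmed lesion is scored; left unscored over that denominator, the shortfall is the full r. Nor is a cumulative measure being imposed: a lesion that has healed and not recurred is healed at the later visit.

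SAP 7.1 also offers an alternative: "Depending on the number of discontinuations and missed visits from the study, a sensitivity analysis might be conducted". Its last-observation rule would generally keep a healed status, but it is optional, depends on discontinuations and missed visits, and does not govern the main analysis.

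Several limits stand. How often filming stops is unknown: X-rays are marked at many visits, and a healed lesion in a bone still filmed stays observed. The Synopsis repeats assessments at End of Treatment, so that visit may be complete if healed sites are re-imaged. The study reference manual cited in Protocol 7.5.1.2 was not available, so the absence of a rule is established only for these two documents.

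A reader might infer that the SAP's final X-ray analysis will understate healing. The documents do not support that. SAP 8.8.2.2 has no healing-category table, and the direction for its lesion counts is not fixed. SAP 8.1 says: "The final analysis will be conducted when all patients enrolled in the study have completed the Week 72 visit or have discontinued the study". The SAP's own schedule labels Week 72 as End of Treatment with X-ray marked, although the healing footnote still applies to that row; under the amended protocol Week 72 is an intermediate visit.

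**Conclusion.** The gap is real and minor. Read literally, the stopping rule and the missing-data rule remove lesions because they healed, and the by-visit percentage healed in Protocol 7.6.1.3 can then fall below the true share. That direction rests on this mechanism alone, with no recurrence; dropout of subjects with unhealed lesions can offset it on an imaged-lesion denominator. The size cannot be derived from the documents, and the percentages above only illustrate it. The shortfall is zero if healed status is retained. The endpoint is exploratory and descriptive, about 20 subjects are enrolled, and the planned listing would show each subject's X-ray history.

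**What to change.** In Protocol 7.6.2.6 and SAP 7.1 and 8.8.2.2:

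1. Add the healing-category table required by Protocol 7.6.1.3 as amended.
2. State, as an exception to the no-imputation rule, that a lesion whose last central reading is healed, and which is then no longer filmed for that reason, counts as healed (0 active) at later visits unless a later film shows otherwise. If filming stopped on a local reading, keep the last central category.
3. Set the denominator at each visit to all baseline active lesions in subjects still in the study, and report how many lesions were actually imaged.
4. State whether filming stops per lesion or per subject.

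The cost is wording and a simple derivation, with no extra films. The downside is that an undetected re-fracture would still count as healed; the number imaged shows how far each percentage rests on carried-forward readings. The rule does not correct for dropout of subjects with unhealed lesions.

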7.5.1.2.2 Patient-reported Outcomes Measurements

Pain, physical function, and physical and mental health will also be assessed using validated PRO instruments, including the WOMAC, the BPI, and the SF-36.

WOMAC: The WOMAC will be completed by subjects pre-dose at Weeks 0, 12, 24, 36, 48, and 72 to assess pain, stiffness, and physical function. The WOMAC consists of 24 items divided into 3 subscales:

- Pain (5 items): during walking, using stairs, in bed, sitting or lying, and standing
- Stiffness (2 items): after first waking and later in the day
- Physical Function (17 items): stair use, rising from sitting, standing, bending, walking, getting in / out of a car, shopping, putting on / taking off socks, rising from bed, lying in bed, getting in / out of bath, sitting, getting on / off toilet, heavy household duties, light household duties

BPI: The BPI will be completed by subjects pre-dose at Weeks 0, 12, 24, 36, 48, 72, 96, 120, and 144 to assess pain severity and the impact of pain on daily functioning. On the BPI, mild pain is defined as a worst pain score of 1 to 4, moderate pain is defined as a worst pain score of 5 to 6, and severe pain is defined as a worst pain score of 7 to 10.

SF-36: The SF36 will be completed by subjects- pre-dose at Weeks 0, 12, 24, 36, 48, 72, 96, 120, and 144 to assess physical and mental health based on 8 scaled scores that are the weighted sums of the questions in their section: vitality, physical functioning, bodily pain, general health perceptions, physical role functioning, emotional role functioning, social role functioning, and mental health. Each scale is directly transformed into a 0 to 100 scale on the assumption that each question carries equal weight. Lower scores indicate more disability and higher scores indicate less disability, i.e., a score of zero is equivalent to maximum disability and a score of 100 is equivalent to no disability.

7.5.1.2.3 Clinical Outcomes Measurements

Gross motor impairment, including diminished walking ability, pain, and muscle weakness are potential complications associated with XLH-related skeletal deformities. Changes in walking ability, lower extremity strength, and agility will be measured by 6MWT and the TUG test pre-dose at Week 0 and while on treatment at Weeks 24, 36, 48, and 72. A trained clinician will administer this assessment following participation in a formal training protocol conducted by the sponsor.

6MWT: The 6MWT assesses walking ability and will be administered in accordance with general principles set forth in the American Thoracic Society (ATS) guidelines ([ATS/ERS 2002](#)). Subjects will be instructed to walk the length of a pre-measured course for 6

consecutive minutes. The total distance walked at the end of 6 minutes will be recorded in meters. The percent of predicted normal values will be calculated using published normative data based on age, and gender (Gibbons et al. 2001).

TUG: The TUG assesses transitions during ambulatory activity incorporating strength, agility, and dynamic balance assessments. The TUG score will be reported as the time (in seconds) that a person takes to rise from a chair, walk three meters (approximately 10 feet), turn around, walk back to the chair, and sit down.

7.5.2 Drug Concentration Measurements

To assess KRN23 concentration and possible accumulation, serum pre-dose levels will be evaluated as a PK parameter in this study. A pre-dose blood sample will be obtained at Weeks 24, 36, 48, 72, 96, 120, 144, and every 24 weeks as applicable through the EoT Visit or at the earliest indicated visit once the necessary approvals have been obtained. For each sample collection, the time elapsed since last study drug administration will be recorded on the eCRF.

7.5.3 Safety Measurements

7.5.3.1 Adverse Events

The investigator will inquire about AEs at all subject visits by asking the subject a question such as: "How have you been feeling since your last visit?" All AEs, whether observed by the investigator or reported by the subject, will be recorded on the appropriate AE page of the eCRF and as appropriate on the SAE form, from the time the subject signs the informed consent through their EoT Visit or final Safety Follow-up TC as outlined in Section 7.1. The Safety Follow-up telephone call (TC) that occurs 4 weeks (+5 days) after a subject's EoT Visit, will collect information on whether KRN23 treatment has been started through another mechanism and, if not, any ongoing or new AEs, SAEs, or concomitant medications. If the subject is not continuing KRN23 therapy under commercial use or another mechanism at that time, then site personnel will initiate a subsequent Safety Follow-up TC 8 weeks (+ 5 days) after the ET Visit to collect information on whether KRN23 treatment has been started through another mechanism and, if not, any ongoing or new AEs, SAEs, or concomitant medications. The determination, evaluation, reporting, and follow-up of AEs will be performed as outlined in Section 8.5. At each visit and the follow-up telephone call, subjects will be asked about any new or ongoing AEs since the previous visit. Assessments of AEs will occur at each visit to the investigational site, all HH visits, and the follow-up telephone call as outlined in Section 7.1. All AEs will be evaluated to determine whether they meet the criteria of being a DLT (Section 7.5.3.13).

Clinically significant changes from baseline in physical examination findings, vital signs, clinical laboratory parameters, renal ultrasounds, eGFR, ECHO, and ECGs will be recorded as AEs or SAEs, if appropriate.

Any laboratory test results that fall outside the laboratory normal range will be considered abnormal. The investigator will indicate if such values are clinically significant (CS) or not (NCS). All laboratory tests with clinically abnormal values (i.e., beyond those expected for subjects with XLH of this age group) should only be recorded as an AE if symptomatic, if potentially life-threatening without symptoms, or if deemed appropriate by the investigator.

If a subject experiences an AE, the subject will receive appropriate treatment and supportive care as necessary, and the investigator will continue to follow up on the AE until there is a return to the subject's Baseline condition or until a clinically satisfactory resolution is achieved.

7.5.3.2 Medical History

General medical information includes subject demographics (date of birth, ethnicity, and sex) and a history of major medical illnesses, diagnoses, and surgeries. The review will also include an assessment of symptoms and conditions associated with XLH and standard of care treatment.

Subjects must be willing to provide access to prior medical records for the collection of historical biochemical and radiographic data, as well as disease history. The specific diagnosis of XLH will be recorded, along with date of onset, clinical presentation, and date and method of diagnosis. A disease-specific list of signs, symptoms, and conditions associated with XLH in adults, as well as any medications administered to manage these conditions, will be completed as part of the medical history.

7.5.3.3 Prior and Concomitant Medications/Therapies

Subjects will be asked whether medication to suppress PTH (e.g., Sensipar®, cinacalcet, calcimimetics) has been taken within 2 months before the Screening Visit; subjects who must continue to take PTH suppressors will be excluded from the study, or, if medically able to discontinue PTH suppressors, the subject may be enrolled after a 2-month washout period. Likewise, a 21-day washout of any active pharmacologic vitamin D metabolite or its analog (e.g., calcitriol, doxercalciferol, and paricalcitol), phosphate, and aluminum hydroxide antacids (e.g., Maalox® and Mylanta®) is required for inclusion if medically able to discontinue those medications. Live (attenuated) vaccines (except influenza vaccines) are prohibited within 3 months prior to Screening through the EoT Visit.

All other medications (investigational, prescription, over-the-counter, and herbal) and nutritional supplements taken within 30 days before the Screening Visit will be reviewed and recorded. Throughout the study, investigators may prescribe any concomitant medications or treatments deemed necessary to provide adequate supportive care except those listed in Section 7.5.3.3.1. Therapies (physical therapy, occupational therapy as well as mobility and walking devices, including ankle foot orthoses (AFOs), braces, cane, crutches, walker, wheelchair etc.) used within 30 days before the Screening Visit and at Baseline will also be reviewed and recorded.

Concomitant medications and therapies while on treatment will be reviewed and recorded in the subject's eCRF beginning on the day of initial dosing (Baseline, Week 0) (indication, start date, stop date, dose, dose regimen), at all clinic and HH visits, and at the follow-up telephone call. At each subsequent visit, change in medications and therapies since the previous visit will be recorded on the concomitant medication pages in the subject's eCRF. Throughout the study, there should be no significant changes to a subject's diet or medication schedule unless medically indicated. Investigators may prescribe any concomitant medications or treatments deemed necessary to provide adequate supportive care, except those listed in Section [7.5.3.3.1](#).

